6.5 Plasma Samples

Plasma samples will be drawn to test for anti-CYT107 antibodies on approximately Days 0 (prior to IL-7 administration), 42, and 100 from the start of IL-7 therapy. The samples will be batched and sent to Revimmune for immunogenicity assays.

6.6 Outside Physician Participation During Treatment

- a) MDACC Physician communication with the outside physician is required prior to the patient returning to the local physician. This will be documented in the patient record
- b) A letter to the local physician outlining the patient's participation in a clinical trial will request local physician agreement to supervise the patient's care.
- c) Protocol required evaluations outside MDACC will be documented by telephone, fax or e-mail. Fax and/or e-mail will be dated and signed by the MDACC physician, indicating that they have reviewed it.
- d) Changes in drug dose and/or schedule must be discussed with and approved by the MDACC physician investigator, or their representative prior to initiation, and will be documented in the patient record.
- e) A copy of the informed consent, protocol abstract, treatment schema and evaluation during treatment will be provided to the local physician.
- f) Documentation to be provided by the local physician will include drug administration records, progress notes, reports of protocol required laboratory and diagnostic studies and documentation of any hospitalizations.
- g) The home physician would only be alerting the Principal Investigator to a subject's life-threatening event (much as a family member would) and the Principal Investigator would be assessing the event per the protocol.
- h) Patients will be evaluated either in person or remotely via telemedicine.

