6.0 Evaluation During Study

Every effort will be made to adhere to the schedule of events and all protocol requirements. Variations in protocol requirements that do not affect the rights and safety of the patient will not be considered as deviations. Such variations may include laboratory assessments completed outside of schedule and occasional missed required research samples. Missed samples for correlative studies will not constitute protocol deviations.

For patients who have discharged to their home clinics, and are not being followed weekly at MD Anderson, labs and assessments will be collected as feasible in their home clinics or upon patient's return to MDACC clinic. Any missed time points will not be counted as protocol deviations.

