7.0 Statistical Considerations

7.1 Outcomes and Covariates

7.1.1 Primary Outcomes

Toxicity. Dose limiting toxicity (DLT) is defined as any of the following events: grade 3 or 4 GVHD, secondary graft failure, disease relapse, development of PTLD, development of PML, grade 2 organ failure or grade 2-4 skin rash, fatigue, AST and ALT elevations, allergic anaphylaxis, or hemolytic anemia, attributable to CYT107, or death, occurring within 42 days of the first CYT107 injection.

Biological Responses. The absolute number and percentage of total White Blood Cells (WBCs) consisting of T-cells and of B-cells will be observed at 1, 3, 6, 9 and 12 months.

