7.3.2 Within-Dose Safety Monitoring Rule

For each dose $d = 1, 2, 3$, denote $p(d) = \Pr(\text{DLT at dose } d)$. Assume that each $p(d)$ follows a beta(.35, .65) prior. Applying the method of Thall et al.⁴¹, enrollment to dose d will be stopped if $\Pr[p(d) > .35 | \text{data}] > .85$. This criterion will be applied continuously starting at $n = 3$, which implies that accrual to d should be stopped if [number of DLTs] / [number of patients evaluated] is greater than or equal to 3/3 or 4/5. To apply this safety rule for each dose to 2 cohorts of size 3 each may or may not require suspension of accrual. For each dose (a) once 1 or more pats in cohort 1 (pats #1,2,3) have “No toxicity” by day 42 of followup, cohort 2 may begin enrollment, and (b) once 2 or more pats in cohorts 1 and 2 combined (pats #1,2,3,4,5,6) have “No toxicity” by day 42 of follow up, the last patient 7 may be enrolled. This rule has the following operating characteristics.

Operating characteristics of the within-dose safety monitoring rule

True $p(\text{DLT} d)$	$\Pr(\text{Stop accrual to } d)$	Sample Size	Quartiles
.35	.163	7, 7, 7	
.55	.497	4, 7, 7	
.60	.601	4, 6, 7	
.65	.607	3, 4, 7	

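### DLTs in discharged patients may be under-counted: home physicians alert only to life-threatening events, and nothing guarantees a completed assessment by day 42

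*Combined protocol and SAP*

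**What the plan says.** Section 7.1.1 makes DLT a primary outcome. The list opens with "grade 3 or 4 GVHD, secondary graft failure, disease relapse, development of PTLD, development of PML" and continues with "grade 2 organ failure or grade 2-4 skin rash, fatigue, AST and ALT elevations, allergic anaphylaxis, or hemolytic anemia, attributable to CYT107, or death", all "occurring within 42 days of the first CYT107 injection".

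Section 6.2 schedules laboratory tests, a physical examination and an adverse event assessment every week to day +42. Section 6.0 then relaxes the schedule for patients who have gone home and are not seen weekly at the centre. For them, "labs and assessments will be collected as feasible in their home clinics or upon patient's return to MDACC clinic", and "Any missed time points will not be counted as protocol deviations". It makes no exception for the DLT window.

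On what the local doctor must report, section 6.6(g) says: "The home physician would only be alerting the Principal Investigator to a subject's life-threatening event". Other items of 6.6 cover how outside evaluations are documented (c), which local records are supplied (f), and evaluation in person or by telemedicine (h).

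Section 7.3.2 uses the DLT data in two ways. A Bayesian rule stops accrual to a dose on the number of DLTs among patients evaluated. Accrual conditions also release further patients: the second cohort at a dose may start "once 1 or more pats in cohort 1" are free of toxicity by day 42 of follow-up, and a similar condition governs the seventh patient.

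**The concern.** Several DLT components can occur without threatening life: grade 2 organ failure, rash, fatigue, raised AST or ALT. The local doctor's alert does not cover them, and the scheduled assessments that would find them can be missed without consequence. CYT107 may start as late as day 180 after transplant, when some patients may already be under local care.

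The plan does not say how to classify a patient whose 42-day assessment is incomplete. A patient with missed visits and no alert could be entered as free of toxicity. That error runs in one direction. It lowers the observed DLT rate, makes the stopping rule less likely to act, and can satisfy an accrual condition that has not really been met. The stopping rule, the accrual conditions and the primary safety result all rest on this count, with seven patients per dose.

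**Working it through.** **1. Routes by which a non-life-threatening DLT at home could reach the investigator**

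| Provision | What it gives | Guarantees an assessment through day 42? |
|---|---|---|
| 6.2 | Weekly tests, examination, adverse event assessment | Scheduled, but within the 6.0 exemption |
| 6.6(c) | How outside evaluations are documented | No; it does not require that they take place |
| 6.6(f) | Local notes, laboratory reports, hospitalization records | No deadline |
| 6.6(g) | Alert from the home physician | Life-threatening events only |
| 6.6(h) | In-person or remote evaluation | No frequency or window; AST/ALT still needs a blood draw |
| 4.0 | Toxicity must be known before doses 2 and 3 | Only to about day 14 |
| 7.7 | Toxicity summaries after 42 days | Reviews whatever was collected |

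The three doses are a week apart (days 0, 7 and 14 on schedule), so the last 42 − 14 = 28 days of the window contain no dosing visit.

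**2. The plan's own stopping probabilities**

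Inputs from 7.3.2: prior beta(0.35, 0.65); stop if Pr(p > 0.35 | data) > 0.85; monitoring from n = 3. With x DLTs in n patients the posterior is beta(0.35 + x, 0.65 + n − x). Seven is the maximum per dose, so stopping saves patients only at n = 3 to 6. The smallest stopping counts are 3/3, 3/4, 4/5 and 4/6.

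Counting paths:
- stop at n = 3: p³
- stop at n = 4 (two DLTs in three, then a third): 3p³(1 − p)
- stop at n = 5: none, because 4/5 cannot be reached without first stopping at 3/3 or 3/4
- stop at n = 6 (two DLTs in four, then two more): 6p⁴(1 − p)²

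At p = 0.55: 0.1664 + 0.2246 + 0.1112 = 0.502.

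| True rate | Computed | Stated in 7.3.2 |
|---|---|---|
| 0.35 | 0.165 | 0.163 |
| 0.55 | 0.502 | 0.497 |
| 0.60 | 0.600 | 0.601 |
| 0.65 | 0.694 | 0.607 |

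Three rows agree to within 0.005. The 0.65 row does not, and no other look schedule tried matched all four rows. It is not used below.

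**3. Effect of one missed DLT (no miss rate needed)**

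| True count | Posterior | Count with one missed | Posterior |
|---|---|---|---|
| 3/3 | 0.985 | 2/3 | 0.834 |
| 3/4 | 0.932 | 2/4 | 0.694 |
| 4/5 | 0.973 | 3/5 | 0.849 |
| 4/6 | 0.929 | 3/6 | 0.746 |

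At each boundary, one missed DLT takes the posterior below 0.85, and the dose stays open at that look.

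**4. Illustration over a range of miss rates**

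Assumption: a share m of all DLTs is missed and those patients are counted as evaluated without DLT, so the observed rate is p(1 − m). For p = 0.55 and m = 0.25 it is 0.4125, and the formula gives 0.070 + 0.124 + 0.060 = 0.254.

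| Share missed | Pr(stop), true 0.55 | Pr(stop), true 0.60 |
|---|---|---|
| 0% | 0.502 | 0.600 |
| 10% | 0.397 | 0.483 |
| 25% | 0.254 | 0.316 |
| 50% | 0.084 | 0.108 |

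The 25% row would arise if, for example, half the patients were at home and half their DLTs went unreported. Neither figure is in the documents.

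**5. Related text**

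Section 9.0 says that isolated GPT and GOT elevations are not captured, although AST/ALT elevation is on the DLT list. The weekly panel in 6.2 names SGPT and ALT, which are the same enzyme, and does not name AST. Section 9.0 also limits REDCap entry to SAEs and to adverse events requiring dose modification.

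**The case against.** Item 6.6(g) can be read narrowly. It describes an unsolicited alert and leaves assessment with the investigator; it does not describe the whole reporting system. Routine ascertainment sits in 6.2 and in 6.6(c), (f) and (h). Section 9.0 collects adverse events to 30 days after the last injection, about day 44 on schedule. Attributable grade 2 non-hematological toxicity delays the next dose under 4.0, so it has to be looked for before doses 2 and 3. The IND Office reviews toxicity summaries under 7.7. Section 6.0 removes deviation status from a missed visit without cancelling the assessment, and its opening paragraph confines the general tolerance to variations that do not affect safety.

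Much of this stands. A reader might infer that the home physician's alert is the only route, or that follow-up is waived; neither is so. What remains is that the home-clinic paragraph of 6.0 carries no safety limit of its own, and no listed route has to produce a completed assessment between about day 14 and day 42.

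A reader might also infer that most DLT components are grade 2 events. Counting AST/ALT as one, 2 of the 12 (organ failure and rash) carry an explicit grade 2 threshold. If the rash grading is carried along the rest of the list, it is 6 of 12. The point needs only that several components are not life-threatening.

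The illustration treats all DLTs as equally easy to miss, whereas death, relapse or severe GVHD would seldom go unseen. If softer events were half of all DLTs and 25% of those were missed (both assumptions), 12.5% would be missed overall. Pr(stop) would then be 0.37 at a true rate of 0.55 and 0.45 at 0.60. The loss is smaller but still material.

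**Conclusion.** The gap is real: an alert confined to life-threatening events, an exemption that reaches DLT assessments, and no rule for an incomplete 42-day assessment. DLTs in discharged patients may be under-counted, and an unassessed patient could be counted as free of toxicity. The text does not show that DLTs are in fact under-counted. The size depends on discharge and miss rates that the documents do not give.

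Under the stated rule with looks at n = 3 to 6, missing 10% of DLTs would cost about 10 to 12 percentage points of stopping probability at true rates of 0.55 and 0.60. Missing 25% would roughly halve it.

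A reader might go on to infer a biased comparison between doses. The documents do not support that. Patients 3 to 21 are randomized, so an uneven home-clinic share among them would be chance imbalance, and 7.5.3 selects the optimal dose on T-cell percentage, not on DLT rates.

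**What to change.** 1. In 6.6(g), have the home physician report any event on the 7.1.1 DLT list through day 42.
2. In 6.0, take the weekly adverse event assessment and the DLT laboratory tests through day 42 out of the feasibility and no-deviation provision. When the patient is at home, use the telemedicine contact already allowed in 6.6(h), with local blood draws.
3. In 7.3.2, count a patient as free of toxicity, and as evaluated without DLT, only after a completed day-42 DLT assessment. A DLT already observed counts at once. A patient with neither stays out of the no-toxicity count and the denominator.
4. Reconcile the section 9.0 statement on isolated GPT/GOT elevations with the AST/ALT component in 7.1.1, and check the 6.2 panel against the result.

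Separately, check the 0.65 row of the operating-characteristics table.

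The weekly assessments are already scheduled, so the change is one of protocol wording. The cost is some logged deviations and an occasional short wait for a day-42 assessment before accrual is released.

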7.0 Statistical Considerations

7.1 Outcomes and Covariates

7.1.1 Primary Outcomes

Toxicity. Dose limiting toxicity (DLT) is defined as any of the following events: grade 3 or 4 GVHD, secondary graft failure, disease relapse, development of PTLD, development of PML, grade 2 organ failure or grade 2-4 skin rash, fatigue, AST and ALT elevations, allergic anaphylaxis, or hemolytic anemia, attributable to CYT107, or death, occurring within 42 days of the first CYT107 injection.

Biological Responses. The absolute number and percentage of total White Blood Cells (WBCs) consisting of T-cells and of B-cells will be observed at 1, 3, 6, 9 and 12 months.

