4.0 Treatment Plan and Study Design

CYT107 will not be administered before Day 60 but could be started as late as Day 180 post-CBT or haplo-SCT.

The active treatment period will be from the first injection of CYT107 and for 30 days after the last injection. The follow-up period will be for three years after the last injection.

Patients will be treated with CYT107 by intramuscular route (I.M.)* post CBT or haplo-SCT (from 60 to 180 days), with 1 of 3 doses below:

- 5 mcg/kg/dose for 3 doses, one week apart
- 10 mcg/kg/dose for 3 doses, one week apart
- 20 mcg/kg/dose for 3 doses, one week apart

Enrollment of the first 3 participants will be staggered by 14 days. Accrual in between cohorts will be halted for 30 days after the last patient in each cohort has received the last dose of CYT107.

* If the patient's platelet count is below 35,000, the product may be administered by subcutaneous route.

All patients will receive foscarnet for the management of CMV infection as per Stem Cell Transplantation and Cellular Therapy Department's standard of care.

Dose modifications

Treatment will be permanently discontinued for patients developing grade 3 or 4 GVHD, secondary graft failure, disease relapse, PTLD, PML, grade 2-4 skin rash, or grade 3-4 non-hematological toxicity attributable to CYT107.

Patients who develop grade 2 non-hematological toxicity attributable to the CYT107 will have the next dose withheld until the toxicity resolves to grade 1. If the toxicity resolves within 2 weeks the drug will be administered at the same dose, however if the toxicity takes more than 2 weeks to resolve the drug will be administered at the next lower level, or permanently discontinued if the patient was already at the lowest level. If the toxicity takes more than 4 weeks to improve to grade 1, the CYT107 will be permanently discontinued

For patients who at study entry have grade 0, 1 or 2 hematological toxicity and develop grade IV hematological toxicity attributable to the CYT107 will have the next dose withheld until the toxicity resolves to grade 2. If the toxicity resolves within 2 weeks the drug will be administered at the same dose, however if the toxicity takes more than 2 weeks to resolve the drug will be administered at the next lower level, or permanently discontinued if the patient was already at the lowest level. If the toxicity takes more than 4 weeks to improve to grade 2, the CYT107 will be permanently discontinued

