7.6 Trial Conduct

The Biostatistics Department Clinical Trial Conduct Website will be used to assign a dose to each patient at enrollment. This will be set up and overseen by a Research Statistician in the Biostat Dept to be designated by [name] prior to re-starting the trial at patient number 3, using a randomization sequence provided by [name]. The Principal Investigator and designated personnel in the SCT Dept will be responsible for recording all baseline covariates and outcome variables and implementing the within-dose stopping rule in terms of DLTs.

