7.7 Summary Reports

The investigator is responsible for completing a toxicity summary report and submitting it to the IND Office, Medical Affairs and Safety Group, for review and approval. This should be submitted after the first, the first three, and the first five evaluable patients per cohort, have completed 42 days post-first CYT107 injection.

A copy of the cohort summary should be placed in the Investigator's Regulatory Binder, under "Sponsor Correspondence".

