8.0 Criteria for Removal from the Study

Any patient can be removed from study for the following:

- Patient withdrawal of the informed consent
- Patient not being compliant
- An increasing or unexpected pattern of toxicity is observed deemed unacceptable by the study chairman
- Grade 2-4 skin rash, grade 3 or 4 GVHD, secondary graft failure, disease relapse, PTLD, PML or grade 3-4 non-hematological toxicity attributable to CYT107
- Disease progression
- Investigator judgment when the well-being and best interest of the patient is compromised
- Secondary Graft Failure
- 1 year after last injection.

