Active treatment period (ATP) is defined from the first injection of CYT107 through 30 days from

the last injection.

Time for Adverse Event (AE) Collection:

Adverse events will be collected from the first injection of CYT107 through 30 days from the last injection. AEs that occur up to 30 days from the last injection of CYT107 will be followed until resolution.

The collection of adverse events will reflect the onset and resolution date and maximum grade. If a patient is taken off study while an event is still ongoing, this will be followed until resolution or the event has stabilized. Pre-existing medical conditions will be recorded only if an exacerbation occurs during the active treatment period. Co-morbid events will not be scored separately.

Adverse Event Reporting:

The Investigator or physician designee is responsible for verifying and providing source documentation for all adverse events, and assigning attribution for each event on all subjects enrolled on this study.

Adverse events will be documented and entered into the electronic case report form (REDCap/CORe). All protocol specific data will be entered into REDCap/CORe.

Events not to be considered adverse events in this study are those related to original disease or expected in the post-allogeneic transplant period.

Isolated changes in laboratory parameters such as electrolyte, magnesium and metabolic imbalances, uric acid changes, elevations of GPT, GOT, LDH and alkaline phosphatase will not be captured.

Concomitant medications

Patients treated on this protocol will require supportive care treatment (concomitant medications). These medications are considered standard of care and have no scientific contribution to the protocol; therefore no data will be captured on various medications needed or their side effects. All concomitant medications will be captured in the medical record.

Causality Assessment.

The principal investigator will be the final arbiter in determining the causality assessment.

List of most common expected adverse events:

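### Attributable grade 3-4 non-hematological toxicities outside the named DLT items end a patient's treatment but do not count toward closing a dose

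*Combined protocol and SAP*

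**What the plan says.** Section 7.1.1 counts as a DLT any of a list of events within 42 days of the first injection. The list starts with grade 3 or 4 GVHD, secondary graft failure, relapse, PTLD and PML. It goes on to "grade 2 organ failure or grade 2-4 skin rash, fatigue, AST and ALT elevations, allergic anaphylaxis, or hemolytic anemia, attributable to CYT107" and closes with death.

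The main discontinuation sentence in section 4.0 starts with the same five events but ends with "grade 2-4 skin rash, or grade 3-4 non-hematological toxicity attributable to CYT107". Section 8.0 gives the same events as grounds for removal, including "PTLD, PML or grade 3-4 non-hematological toxicity attributable to CYT107".

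Section 7.3.2 defines p(d) as the probability of DLT at dose d. Accrual to a dose stops when the posterior probability that p(d) exceeds .35 is above .85, checked continuously from the third patient. The section prints this as a ratio of DLTs to evaluated patients that "is greater than or equal to 3/3 or 4/5". Section 7.6 makes the investigator's team responsible for "implementing the within-dose stopping rule in terms of DLTs".

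Two other controls matter here. Under 7.3.2, once at least one of the first three patients at a dose "have “No toxicity” by day 42 of followup, cohort 2 may begin enrollment", and patient 7 may enter once at least two of the first six are clear. Section 7.7 has the investigator complete a toxicity summary after the first, third and fifth evaluable patients, "submitting it to the IND Office, Medical Affairs and Safety Group, for review and approval".

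**The concern.** An attributable grade 4 event that is not on the list stops that patient's drug but is scored as a non-DLT, whereas an attributable grade 2 rash is scored as a DLT. Grade 3 hypertension or a grade 3 arrhythmia without organ failure would be examples. They are suggested by the conditions screened in section 3.2 and are not reported toxicities of CYT107. No section explains the difference.

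Safety is half of the primary objective, and section 7.5.3 selects the optimal dose on T-cell percentage alone. The DLT rule is therefore the only prespecified numerical safety criterion that acts on a dose. With seven patients per dose, one event scored the wrong way can keep a dose open.

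**Working it through.** **Step 1. The lists side by side.**

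| Event | Ends treatment (4.0 list sentence, 8.0) | DLT (7.1.1) |
|---|---|---|
| Grade 3-4 GVHD, graft failure, relapse, PTLD, PML | yes | yes |
| Grade 2-4 rash | yes | yes |
| Attributable grade 3-4 fatigue, AST/ALT elevation, anaphylaxis | yes | yes, by name |
| Attributable grade 3-4 organ failure | yes | only grade 2 is printed |
| Any other attributable, non-fatal grade 3-4 non-hematological toxicity | yes | no |

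A fatal toxicity enters as death. The gap is the last row and, read literally, the row above it.

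**Step 2. The rule.** With the beta(.35, .65) prior, x DLTs in n patients give a beta(.35 + x, .65 + n − x) posterior. Its probability above .35, at the lowest count that stops and one event below, is:

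| n | Stops at | Posterior | One fewer | Posterior |
|---|---|---|---|---|
| 3 | 3 | .985 | 2 | .834 |
| 4 | 3 | .932 | 2 | .694 |
| 5 | 4 | .973 | 3 | .849 |
| 6 | 4 | .929 | 3 | .746 |

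At each of these counts, one event scored as a non-DLT turns a stop into a continue.

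**Step 3. Reproduce the plan's table.** Looks are after patients 3 to 6, since a stop at patient 7 saves no accrual. Once 3/4 is enforced, 4/5 cannot be reached, so

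Pr(stop) = p³ + 3p³(1 − p) + 6p⁴(1 − p)²,

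the terms being stops at 3/3, 3/4 and 4/6.

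- p = .35: .043 + .084 + .038 = .165 (plan: .163)
- p = .55: .166 + .225 + .111 = .502 (plan: .497)
- p = .60: .216 + .259 + .124 = .600 (plan: .601)

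The .65 row does not reproduce (.694 against .607). That is a separate matter and is not used here.

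**Step 4. Illustrate the effect.** The documents give no rate for off-list events, so the rates below are assumed. Patients with an off-list event are taken to have no listed DLT; overlap would shrink the differences.

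- Listed rate .20, off-list .05. Scored as now: .0080 + .0192 + .0061 = .033. All counted (p = .25): .0156 + .0352 + .0132 = .064.
- Listed rate .50, off-list .05. Scored as now: .1250 + .1875 + .0938 = .406. All counted (p = .55): .502.

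**Step 5. Sensitivity to the look schedule.** Section 7.4 speaks of early stops only at 3 or 6 patients. With looks there only, Pr(stop) = Pr(at least 4 of 6) + p³(1 − p)³.

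- p = .20 and .25: .0170 + .0041 = .021, and .0376 + .0066 = .044.
- p = .50 and .55: .3438 + .0156 = .359, and .4415 + .0152 = .457.

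The levels fall but the differences stay about the same.

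**Step 6. Do the enrollment gates make up for it?** The plan does not define "No toxicity". If it means no DLT, the gates ignore off-list events too. If it is read literally, a patient with an off-list event is not clear, so 2 listed DLTs plus 1 off-list event in three patients would hold cohort 2. But at 3/4 the gate for patients 4-6 has already been passed, and at 4/6 two patients are clear, so patient 7 may enter. At p = .55, .225 + .111 = .336 of the .502 arises at those two counts. In the .50 plus .05 case, counting literal holds as stops raises .406 to .428. That recovers .022 of the .096 shortfall.

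**The case against.** The case for leaving the list alone has several parts.

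- **The lists serve different purposes.** One governs a single patient's dosing and the other closes a dose, so they need not match. This stands. But the shared items run in the same order and no reason is given for dropping the last, so a drafting slip is at least as likely as a choice.
- **The gap is narrow.** Rash, fatigue, AST/ALT elevations, anaphylaxis and death are all counted, several of them from grade 2. The expected events in section 9.0 are GVHD and secondary graft failure, and the earlier phase I study summarized in section 2.2 reported good tolerability. This stands: the documents do not show that off-list events will occur.
- **The .35 limit and its table were set for DLT as defined.** Calling the wider endpoint the correct one is a judgment. This also stands, and it is a reason to treat the probabilities above as illustrations.
- **Other safeguards exist.** These are the gates, the 30-day accrual halt between cohorts in 4.0, reporting of all serious adverse events to the IND Office within 5 working days, and the 7.7 review. They make it likely that a serious off-list event is seen and could prompt action. None of them changes the DLT count.
- **The 3/4 and 4/6 boundaries are not printed.** The plan prints only 3/3 and 4/5. However, they follow from the posterior criterion applied continuously, and they reproduce three of the four table rows.

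A reader might infer that every attributable grade 3-4 non-hematological toxicity escapes p(d). The named items and death contradict that. Nor does the affected patient keep receiving drug, since 4.0 stops it.

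**Conclusion.** The gap is real and limited. Non-fatal, attributable grade 3-4 non-hematological toxicities outside the named items end treatment under the list sentence in 4.0 and are grounds for removal under 8.0, but they do not enter p(d). The organ-failure item, as printed, adds to the gap; if a threshold of grade 2 or higher is meant, the gap is smaller but remains. The comparison concerns that one sentence of 4.0, because later paragraphs there add further discontinuation triggers, such as toxicity that is slow to resolve.

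The firm quantitative statement is that a single event can decide whether a dose closes. A reader might go further and conclude that the safety rule loses a known, large share of its stopping probability. The documents do not support that, because the frequency of off-list events is unknown. At low rates the absolute change is small (.033 against .064), and the larger change (.406 against .502) assumes a total rate of .55 and no overlap with listed DLTs. The point merits a correction to the primary safety endpoint. It does not invalidate the design.

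**What to change.** In section 7.1.1:

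- Change the organ-failure item to grade 2 or higher, or to whatever grade is intended.
- Add an item for any other non-hematological toxicity of grade 3 or 4 judged attributable to CYT107, in the same 42-day window. Exclude the isolated laboratory changes that section 9.0 does not capture ("Isolated changes in laboratory parameters such as electrolyte, magnesium and metabolic imbalances" and the others named there).
- Keep AST and ALT elevations as a listed DLT, and say that they are recorded for this purpose. Section 9.0 puts isolated GPT and GOT elevations among the changes that are not captured, so without this statement a listed DLT could go unrecorded.

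If the sponsor means to keep such events out of p(d), 7.1.1 should say so and give the reason.

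The cost is a short amendment. The stopping rule itself is unchanged. Observed DLT rates, and with them the chance of closing a dose, may rise slightly, and the .35 limit would apply to a slightly wider endpoint. How much wider depends on which attribution categories in 9.0 count as attributable, which is worth stating in the same edit.
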